In the literature, there are varying studies as to the effectiveness of LA intraoperatively in controlling post-operative pain in GA dental cases. In Morbidity following dental treatment of children under intubation general anesthesia in a day-stay unit, it was seen that children who were given LA during GA were more likely to experience postoperative dizziness following LA. (Atan et al., 2004)The Effect of Local Anesthetic on Quality of Recovery Characteristics Following Dental Rehabilitation Under General Anesthesia in Children showed no difference for need of postoperative pain medication between those groups that received LA and those that did not. Additionally, in this study they found that 20% of children treated under GA perceived postoperative discomfort due to the sensation of numbness. (Townsend, Ganzberg, & Thikkurissy, 2009)In Perioperative local anesthetic in young pediatric patients undergoing dental extractions under outpatient 'short-case' general anesthesia it was noted pain/discomfort and anxiety were not significantly different between the groups that received LA perioperatively under GA and those that did not (Leong, Roberts, & Ashley, 2007)This result was also observed in Local Anesthesia Effects on Postoperative Pain after Pediatric Oral Rehabilitation Under General Anesthesia where post-operative pain in patients undergoing GA was measured with the UPAT scale and found no statistically significant difference in post-operative pain between the two groups(Moness Ali & Hammuda, 2019).

In Local Anesthesia Affects Physiological Parameters and Reduces Anesthesiologist Intervention in Children Undergoing General Anesthesia for Dental Rehabilitation a statistically significant difference was seen in end tidal CO2 in the cases where dental extractions were performed. It was found that usage of LA in these cases showed better stability of EtCO2. No statistically significance was found in observed respiratory rate and heart rate(Watts, Thikkurissy, Smiley, McTigue, & Smith, n.d.). Very limited research is available on this subject and more research is needed to confirm the validity of the results of this study.

American Academy of Pediatric Dentistry. (2004). Clinical guideline on the elective use of minimal, moderate, and deep sedation and general anesthesia for pediatric dental patients. *Pediatric Dentistry*, 26(7 Suppl), 95–103. Retrieved from <http://www.ncbi.nlm.nih.gov/pubmed/15656444>

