**2. If this is a multi-Center Project, what is the maximum anticipated number of subjects across all sites?**

This study will take place at VCU Children's Hospital of Richmond through the Children's Pavilion and Brook Road Sites. The maximum number of anticipated participants between both sites is 60 children.

**3. \* Provide justification for the sample size by explaining how you arrived at the expected number of participants and why this number is adequate for answering the research questions:**

This is the maximum anticipated participants that we believe we will be able to treat within our expected study timeline. We also believe that 60 participants will provide enough data to adequately answer our research questions.

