**See the help text for additional guidance**

This study has been modeled as a double-blinded randomized control trial. Patients will include healthy children (ASA 1 or ASA 2) without any history of behavioral issues under the age of 6 who had been treatment planned to have exclusively; restorative work, prefabricated crowns and space maintainers.

Dental treatment will be performed under general anesthesia at the Children's Hospital of Richmond Brook Rd. and Children's Pavilion Campuses. Sixty candidates will be recruited from patients presenting for or needing full mouth dental rehabilitation. Patients will be recruited by doctors from VCU Pediatric Dental Clinic and Children's Hospital of Brook Rd. Pediatric Dental Clinic during GA consultation appointments. Participant information will be collected and enclosed in a Google Doc Sheet on Secure VCU Server. Patients will be assigned a participant number which will be used to randomize participants and de-identify patient information. Patients will be randomized into two groups; those that receive LA while under GA and those that will not.

Day of surgery, patients will be evaluated preoperatively using the FLACC pain/behavior scale by the preoperative nurse who is blinded to the candidates group in the study. Intraoperatively, patients will be given either local anesthetic (2% Lidocaine with 1:100,000 epi) infiltration at six sites (once at each of the 6 sextants, L posterior, anterior, R posterior on each arch) of the mouth by the dental surgeon performing the surgery or no local anesthesia will be utilized. Administration of local anesthetic will be a weight based calculation and will be locally infiltrated 10 minutes prior to the end of the procedure. Postoperatively patients will be evaluated in the Post Anesthesia Care Unit (PACU) by a nurse blinded to the intervention before discharge using the same initial pain/ behavior scale, the FLACC scale, used preoperatively. Patients will then be discharged to home when stable and parents of patients will then be given a standard set of post-operative instructions encompassing instructions for the possibility of anesthetized tissues (see documents). Patient's time in the PACU will be noted upon discharge. Lastly, that evening parents were asked to evaluate their children over the phone using a parent administered post- operative evaluation, the Parent's Post-Operative Pain Measure (PPPM).

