**See the help text for additional guidance**

As part of the study patients will be assigned local anesthetic protocol based upon treatment group. Local anesthesia use in dental cases under general anesthesia varies greatly from provider to provider. Ordinarily provider preference would dictate use. No alteration will be made to local anesthesia routine use. Standard infiltration volumes will be used in this study and will be administered based on a weight-based calculation. Location of local anesthetic will be infiltrated in all 6 sextants of the oral cavity. No additional medical tests will be performed as part of the study. As part of the study patients will have a pre- and post operative FLACC score pain assessment. This is a standard pain assessment that is routinely preformed by nursing staff regardless of participation in the study upon patient arrival and before patient departure. Next, throughout the study the patient will be observed by the anesthesiologist throughout the procedure as customary and the anesthesiologist will intervene as customary by deepening the anesthetics if needed. As part of the research patients will be contacted by postoperative phone call which is customary, however as part of this phone call parents will be asked questions to assess patients post operative pain using the parents post operative pain measure tool which is not customary and data will be solely collected for research.

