## Secondary Data/Specimen Details

1. \* Describe the source(s) and nature of the information/specimens being obtained. This response should:

- a. Identify where the data/specimens will come from (e.g., another researcher's registry, pathology lab, commercial source, medical records, etc.); and
- b. List what types of specimens will be obtained (when applicable); and/or
- c. List all data elements that will be obtained (when applicable). A data collection form or other documentation may be uploaded and referenced here.

Data will be collected in a data collection packet. Pre-operatively Nurses in Pre-Op will record FLACC score from the patients chart into the data collection packet. Post- operatively Nurses in Post-op will record FLACC score from the patients chart into the data collection packet. Time in PACU will also be collected.

2. \* Describe whether any agreement exists between you and data/specimen provider that states you will never have access to the ability to identify the participants (i.e. access to identifiers or the code key) and that you will not attempt to re-identify individuals.

Information collected throughout the study on the data collection form will be de-identified and labeled with participant number. Patient identifiers will be stored on secure VCU google drive including patient name, mrn, date of birth, day of surgery, participant number and patient phone number. Patient data will not be re-identified. Patient identifiers will be used merely to access data from the anesthetic record and dental record.

3. \* When the information/specimens were originally collected, did individuals provide consent for secondary research use of their data/specimens (i.e. consent to another research study or to a research registry)?

Yes

No

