## Risks, Discomforts, Potential Harms and Monitoring

1. \* **Describe the risks of each research procedure to participants or others. For each identified risk, provide an assessment of the anticipated seriousness and likelihood of the risk. Some examples of possible risks include but are not limited to:**

- **Physical risks (e.g. bodily harms or discomforts, side effects, etc.)**
- **Psychological risks (e.g. emotional, mental, or spiritual harms or discomforts, changes to thoughts, beliefs, or behaviors, etc.)**
- **Research data risks (e.g. loss of confidentiality and privacy)**
- **Social or legal risks (e.g. impacts on relationships or reputation, legal or criminal justice actions for self or others, etc.)**
- **Financial risks (e.g. impacts on income, employability, or insurability, loss of services, etc.)**
- **Other risks (e.g. unforeseeable risks of experimental procedures, risks related to particular study designs (randomization, washout, placebo, withholding care/services, deception), etc.)**

See the help text for additional guidance.

Local anesthesia is routinely used in dental treatment and can lead to short term post operative numbness. In patients that will receive local anesthesia they will have transient numbness that can lead to some discomfort due to the temporary altered sensation in the area. Additionally due to the numb sensation some patients can cause inadvertent self inflicted trauma in the area. Additionally, throughout the course of this study there is a risk of loss of confidentiality thorough lost or shared information. Last, anticipate the risk of survey completion that being asked survey questions may cause distress or anxiety since their child will be evaluated. In addition, as part of a randomized control trial groups will be randomized using block randomization- participants will not be able to choose their protocol once enrolled in the study.

2. \* **Describe how each of the risks/harms/discomforts identified above will be minimized:**

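### Lip, cheek or tongue biting after local anesthesia is named as a risk, but no described measure counts it by arm, and numbness distress is seen only inside net pain and behaviour scores

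*Combined protocol and SAP*

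**What the plan says.** Item 1 of Risks, Discomforts, Potential Harms and Monitoring names two physical risks of the local anesthetic. Recipients will have "transient numbness that can lead to some discomfort due to the temporary altered sensation in the area", and "some patients can cause inadvertent self inflicted trauma in the area". Item 2 of that section answers with advice: parents in both arms are told that the mouth may be numb and to watch for biting. The same item describes the home survey as covering usual postoperative questions, with diet, activity and pain management as examples. Item 4 provides for clinical monitoring and intervention by the dentist, anesthesiologist and nurses. It does not describe data capture.

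The background (Background, Rationale and Goals, item 1) reports from an earlier study that "20% of children treated under GA perceived postoperative discomfort due to the sensation of numbness".

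The measures described are these:

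- Study Procedures, items 6 and 7: FLACC before surgery and in PACU, time in PACU, and a phone PPPM the same evening. The call itself is customary. The research addition is that "parents will be asked questions to assess patients post operative pain using the parents post operative pain measure tool".
- Secondary Data/Specimen Details, item 1: FLACC scores copied from the chart into a data collection packet, and "Time in PACU will also be collected". Item 2 says that the anesthetic and dental records will be accessed, without listing items.

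No section describes recording numbness, numbness distress, biting or adverse events by arm.

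**The concern.** The title concerns postoperative comfort, and the aims speak of pain control and irritability. The two named harms of the intervention both bear on comfort, and both fall mainly or only on the treated arm. The injections go to all six sextants shortly before the end of the procedure, so treated children may well be numb when scored in PACU and for part of the time that the parents rate.

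Two different things are lost. A bitten lip or tongue has no place in a FLACC score, a PACU time or a PPPM total, so it would not be counted. Numbness distress is visible, but only as behaviour: an upset, numb child and a child in pain can both score higher. The between-arm difference is then a net effect whose parts cannot be separated. A null result could be no benefit, or a benefit offset by numbness, and the described data would not say which.

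**Working it through.** **Plan's own figure.** The only stated number is the sample size: "The maximum number of anticipated participants between both sites is 60 children". Its justification is feasibility and the statement "We also believe that 60 participants will provide enough data to adequately answer our research questions". No alpha, power, effect size, SD or dropout is given, so 60 cannot be reproduced.

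**Named risks against described measures.**

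| Named risk | Handling in the risk section | Described measure that would identify it |
|---|---|---|
| Biting or soft-tissue injury | Advice to parents | None |
| Numbness discomfort | Advice to parents | None directly; may raise FLACC or PPPM |

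**Inputs for the illustration.**

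- *n* = 30 per arm. This is an assumption. The plan says "Patients will be randomized into two groups; those that receive LA while under GA and those that will not" and mentions block randomization, but states no ratio; 60 is a maximum, and children can be withdrawn after consent.
- Biting rate: none is given anywhere, so 2%, 5% and 10% are assumed.
- Numbness discomfort: the 20% quoted from the background.

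**What recording bites would show.** The chance of at least one case among *n* treated children is 1 − (1 − *p*)^*n*:

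- *p* = 2%: 1 − 0.98^30 = 0.45
- *p* = 5%: 1 − 0.95^30 = 0.79
- *p* = 10%: 1 − 0.90^30 = 0.96

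With no cases, the two-sided exact 95% upper limit is 1 − 0.025^(1/*n*):

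- *n* = 30: 11.6%
- *n* = 25: 13.7%
- *n* = 20: 16.8%

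**What recording numbness distress would show.** If the cited 20% applies to treated children, 0.20 × 30 = 6 are expected; the Clopper-Pearson 95% CI for 6/30 is 7.7% to 38.6%. The wording does not fix the denominator. If the 20% covers a whole sample split 1:1 and arises only in children given local anesthesia, the treated-arm rate is 0.20 / 0.50 = 40%, or 12 of 30.

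**Is a test realistic?** For 20% against an assumed control rate of about 0%, 2% or 5%, Fisher's exact test at two-sided 0.05 with 30 per arm has power 57%, 41% or 24%. The items would support estimates with intervals, not a powered comparison.

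**How offsetting works.** Suppose that the injection lowers the mean score by *b*, and that numbness adds *h* points in a fraction *q* of treated children. The net shift is −*b* + *qh*. With *q* = 0.20, numbness adds 0.2, 0.4, 0.6 or 0.8 points to the arm mean for *h* = 1, 2, 3 or 4. A benefit of the same size would be hidden. The values of *h* are illustrative.

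**The case against.** **The call is not limited to pain.** A reader might infer that the evening call asks about nothing else. The risk section does not support this, since it describes usual postoperative questions with diet and activity among the examples. This stands. None of the named examples is numbness or biting, however.

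**Absence from the text is not absence from the forms.** The data collection packet, anesthesia chart, FLACC form and PPPM form are listed as uploads but not reproduced. The list of study-specific activities answers a question about research versus routine care, and the secondary-data section omits the PPPM, so neither is a full field list. This also stands. The supportable statement is that no section describes recording these harms.

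**Distress is already in the outcome.** A tempting stronger reading is that the trial can report the benefit and none of the harm. That goes too far for distress. If it raises the behaviour scores, the arm difference already includes it, and net comfort is arguably what the title asks about. What is lost is attribution. For biting the objection fails, because none of the described scores counts it.

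**Parents may not be able to tell numbness from pain.** Parents in both arms are warned of numbness, and the children are under 6. This is fair, and it makes the distress item secondary.

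**The risks are not ignored.** All parents get the same advice, and clinical staff monitor and intervene. True, but that is care and not a count by arm.

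**Conclusion.** The point holds as a cheap improvement, centred on biting. On the text available, the plan names two physical harms of the local anesthetic, advises parents about them, and describes recording neither. Bites would go uncounted by arm. Numbness distress would be mixed into FLACC and PPPM, and a null result could not be told apart from benefit offset by numbness. The pain comparison itself can still be run.

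The figures are illustrations. The 30 per arm, the biting rates and the application of the cited 20% to treated children are all assumptions. Even with full recording, zero bites in 30 would exclude only rates above 11.6%. A reader might infer that about 6 treated children are predicted to have numbness discomfort, or that a null result would show cancelling effects. The documents support neither: the denominator of the 20% is unclear, and offsetting is a possibility that the described data cannot confirm or exclude.

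**What to change.** On the existing evening call, after the PPPM is complete, ask parents in both arms the same two yes/no questions:

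1. Main item: has the child bitten the lip, cheek or tongue since surgery?
2. Secondary item: has the child seemed distressed by numbness? State in the plan that parents may not be able to separate this from pain.

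Report counts and risk differences by arm with exact 95% CIs next to the pain outcomes, as descriptive results without a test. If the data packet already holds such items, name them in the protocol and plan their reporting by arm.

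The cost is about a minute per call and two data fields. The questions disclose nothing about allocation, since all parents receive the same numbness instructions. The answers may hint at the arm, and asking them last keeps them from influencing the PPPM or its scoring.

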**5. \* List the study exclusion criteria:**

In this study we will exclude children with any sensory or behavioral issues, as this may greatly distort data gathered. We will exclude patients requiring extractions or surgical procedures as local anesthesia may be more beneficial in these patients for pain and hemostasis control intraoperatively. In addition, we recommend the anesthesiologist not to give post-operative Precedex or Ketorolac as it is not standard of care. Patients given Precedex or Ketorolac post-operatively by the anesthesiologist will be withdrawn from the study.

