**2. Recruitment procedures to invite participation in the study (when applicable):**

- How each of the written or verbal recruitment materials and reminders (selected above) will be used
- Who will contact, approach, or respond to potential participants
- Locations where recruitment procedures will take place
- The timing and frequency of recruitment attempts

**3. Eligibility screening prior to consent and how those activities will be carried out (when applicable)****See the help text for additional guidance.**

Patients will be recruited from patients presenting for or needing full mouth dental rehabilitation. Patients will be recruited by doctors from VCU dental clinic and Brook Rd. Clinic during GA consultation appointment. Patients who could be potential research participants will be given information about the research day of their consultation as well as a consent form to review on their own time. Potential participant information will be collected and enclosed in a Google Doc Sheet on VCU account. This would include just patient date of birth, name, MRN, phone number and surgery date. Patients identified as potential research candidates will be approached day of surgery with the option to participate in

the research. At time of consent DOS patients will be assigned a participant number which will be used to mark record and randomize participants. This participant number will correspond to the initial demographics collected. No additional screening activities will be done as we already have a high volume of consultations coming through our clinics.

**5. \* Does this study have a separate protocol document (i.e. a multisite or sponsor's protocol) that contains a detailed description of the study's methodology?**

Yes  
 No

**6. \* Since a separate protocol document is not uploaded, describe the proposed research using language understandable to those IRB committee members whose expertise is not scientific. The description must include:**

- 1. A statement explaining the study design**
- 2. A detailed description of all the procedures that will be followed to carry out the study, preferably in sequential order, and in sufficient detail that the study's methods could be replicated**
- 3. The schedule and frequency of when and how procedures will be conducted (e.g. in person, online, phone, paper, etc.)**

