These risks will be minimized by first, all parents will be provided the same written and verbal post operative instructions including information advising parents that portions of the child's mouth may be numb and they should monitor them closely for the next few hours to ensure of no lip of tongue biting. Second, clinical data stored will be de-identified and stored on a secure VCU server database. Lastly, surveys performed on child will be done through pure objective scale. No questioning will be directed towards child. At home survey will be directed at parents and includes commonly utilized post operative questions to assess how a child is doing after surgery and provide the best post operative guidance (ex. diet, activity, pain management). To minimize the risk of bias block randomization will be utilized and patients will receive post operative instructions encompassing post operative guidance (e.g post operative instructions reviewing local anesthesia will be given to all participants even if it was not utilized.)

3. \* **Describe any potential risks or harms to a community or a specific population based on study findings (e.g. information that could be stigmatizing or derogatory):**

No potential risks or harms to a specific community anticipated.

4. **Where appropriate, discuss provisions for ensuring necessary medical, professional, or psychological intervention in the event of adverse events to the subjects:**

Patient will be monitored by both dentist and anesthesiologist throughout the entirety of the case and monitored by the nurses post operatively. Any medical interventions will be performed by these personnel if necessary. No psychological intervention anticipated.

5. \* **Describe criteria for when the investigator would withdraw an individual participant from the study; such as safety or toxicity concerns, emotional distress, inability to comply with the protocol, etc.:**

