After a patient has been accepted in the study and consent obtained patients will only be withdrawn if it is determined during comprehensive exam under GA if a patient requires EXT of any teeth. In that case patient will have local anesthesia administered in the area of extraction, extraction will be performed and patient will be withdrawn from the study. Patients given Precedex or Ketolorac post-operatively by the anesthesiologist will be withdrawn from the study. These are given based on anesthesia provider's preference. The protocol will discourage the use of these medications for study participants as it would alter the effects of the intervention.

6. \* **Summarize any pre-specified criteria that would trigger the investigator/sponsor/monitoring committee to stop or change the study protocol due to safety concerns:**

None anticipated. Study is evaluating methods that are currently utilized to evaluate which has better patient response. No safety concerns anticipated as lidocaine 2% with 1:100,000 epi is routinely used by some providers in FMDR under GA.

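### Children given post-operative Precedex or Ketorolac are withdrawn after randomisation and treatment, which biases the comparison if use depends on pain

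*Combined protocol and SAP*

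**What the plan says.** The rule appears twice. Under the exclusion criteria (Study Population, item 5): "Patients given Precedex or Ketorolac post-operatively by the anesthesiologist will be withdrawn from the study". Under the withdrawal criteria (Risks, Discomforts, Potential Harms and Monitoring, item 5) it is repeated almost word for word: "Patients given Precedex or Ketolorac post-operatively by the anesthesiologist will be withdrawn from the study", with the explanation "These are given based on anesthesia provider's preference". Both places discourage these drugs; the second adds that they would change the effect being studied.

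The order of events is as follows.

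- **Randomisation:** on the day of surgery. "At time of consent DOS patients will be assigned a participant number which will be used to mark record and randomize participants" (Study Procedures, item 4).
- **Exposure:** a single infiltration 10 minutes before the end of the procedure, or nothing (Study Procedures, item 6).
- **Outcomes:** FLACC in the PACU before discharge, time in PACU, and the PPPM by telephone that evening (same item).

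This is the only stated exit after the exposure. Need for extraction is found at the examination under general anesthesia, and families may withdraw only until the child leaves the pre-operative area (Data Retention, item 3). No section says that withdrawn children are still scored, that their scores are kept, or that children are analysed in the arm assigned. There is no statistical analysis section.

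**The concern.** Withdrawal here depends on something that happens after treatment. Randomisation balances the arms at entry; it does not balance the children who remain once some have been removed for a post-operative event.

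Provider preference says who decides, not that the decision ignores the child's state or arm. The drugs are given when pain and irritability, the study's stated targets, can be seen. The plan says "This study has been modeled as a double-blinded randomized control trial", but only the nurses are described as blinded: "Postoperatively patients will be evaluated in the Post Anesthesia Care Unit (PACU) by a nurse blinded to the intervention before discharge". No sham is described; the infiltration is given "by the dental surgeon performing the surgery or no local anesthesia will be utilized". The anesthesiologist, who gives the drugs, is present when only one arm is infiltrated: "Patient will be monitored by both dentist and anesthesiologist throughout the entirety of the case".

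Three outcomes are possible:

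- Use unrelated to the outcome: no bias, some loss of precision.
- Use follows pain by the same rule in both arms: no bias if LA does nothing; dilution if LA works, because more high-scoring children leave the no-LA arm.
- Use follows pain and the rule also differs by arm: bias in either direction, even if LA does nothing.

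Unrelated has to hold for each outcome analysed. Use driven by agitation or slow recovery would disturb the irritability and PACU-time comparisons too.

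**Working it through.** **The plan's own figure.** The total of 60 is a feasibility maximum (Study Population, items 2 and 3), with no alpha, power, effect, SD or dropout. It cannot be reproduced, so what follows shows what the rule can do and does not estimate what it will do.

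**Assumed inputs.** 30 per arm (1:1), pooled t-test, two-sided 5%. Pain score N(0,1) without LA and N(-0.74,1) with LA. P(drug) = 1/(1+exp(-(base + slope × score))). Slope 0 means use unrelated to pain.

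**Reference.** Noncentrality = 0.74/√(2/30) = 2.87 on 58 df; power 80.5%.

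**Under withdrawal.** Remaining n per arm = 30 × (1 - use). Standardised effect = difference in remaining means / √(mean of the two remaining variances). Power is from the noncentral t. Lost sample alone uses the reduced n with the full 0.74.

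| Use, no LA v LA | Slope | Effect kept | Power, withdrawal | Lost sample alone | Power keeping all, drug lowers score by 1 SD |
|---|---|---|---|---|---|
| 7% v 7% | 0 | 100% | 77.5% | 77.5% | 78.0% |
| 7% v 3.6% | 1 | 98.0% | 76.5% | 78.2% | 78.5% |
| 7% v 2.3% | 2 | 95.6% | 74.8% | 78.5% | 79.0% |
| 7% v 1.8% | 3 | 94.3% | 73.8% | 78.6% | 79.3% |
| 11.9% both | 0 | 100% | 75.1% | 75.1% | 76.5% |
| 15.5% v 8.6% | 1 | 96.0% | 71.5% | 75.0% | 76.1% |
| 22.5% v 9.6% | 2 | 89.1% | 62.8% | 72.8% | 75.0% |
| 28.3% v 11.3% | 3 | 83.7% | 55.2% | 70.5% | 74.0% |

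The last column takes the largest drug effect considered. With no drug effect, keeping everyone gives the reference 80.5%. At low use the expected numbers are about 30 × 0.07 = 2 children v 30 × 0.02 to 0.04 = 1 child.

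**No true LA effect, use differing by arm (more in the no-LA arm), slopes 0 to 3.** Both biases make LA look worse.

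| Use | Withdrawal: bias (SD) | Withdrawal: false positives | Keeping all, 1 SD drug effect: bias (SD) | Keeping all: false positives |
|---|---|---|---|---|
| 20% v 5% | 0, 0.13, 0.20, 0.24 | 4.9%, 7.5%, 10.7%, 12.8% | 0.14, 0.16, 0.17, 0.17 | 8.6%, 9.2%, 9.6%, 9.9% |
| 7% v 2% | 0, 0.05, 0.07, 0.09 | 5.0-6.2% | 0.05 throughout | 5.3-5.5% |

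**Second check on other assumptions.** In a large simulation with overall use of 10, 20 or 30%, a true 0.5 SD shrank to 0.47, 0.45 and 0.43 SD at slope 1, and to 0.42, 0.38 and 0.35 SD at slope 2. Bias was 0.00 whenever use was unrelated to pain, including when it differed by arm. It was also 0.00 when LA had no effect and both arms followed the same pain rule.

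**The case against.** The case for leaving the rule alone has four parts.

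1. **The stated mechanism is preference.** If preference is unrelated to pain, withdrawal is unbiased. Keeping everyone then gains only 0.5 to 1.4 power points when the drug effect is 1 SD (78.0% v 77.5%; 76.5% v 75.1%). With 20% v 5% use and no LA effect, keeping everyone creates a 0.14 SD difference where withdrawal creates none.
2. **Keeping everyone also dilutes.** With a 1 SD drug effect and slope 1, the raw difference is 0.706 SD keeping all v 0.710 SD withdrawing (low use), and 0.671 v 0.682 (higher use). The power gain there comes from sample size.
3. **The model is a worst case.** It makes the pain that triggers the drug identical to the score analysed, although FLACC and PPPM are taken at their own times. At an assumed correlation of 0.5, the 20% v 5% null bias under withdrawal falls to 0.06-0.11 SD and false positives to 5.6-6.7%.
4. **The sponsor may want the effect of LA without these drugs.** Use is also discouraged, so few children may be affected.

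All of these stand as limits on size. They do not remove the point. Nothing in the plan secures independence from pain or arm, and excluding recipients answers the sponsor's apparent question without bias only if that independence holds. At slopes 2 and 3 keeping everyone also dilutes less, and it had the higher power in every true-effect scenario tried. Point 1 is a real cost, and the reason to report use by arm and retain the exclusion analysis.

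**Conclusion.** The concern holds, as a risk and not a demonstrated bias. The plan removes children for an event after randomisation and exposure, with no follow-up and no as-randomised analysis. Whether that biases the result depends on why the drugs are given, which the documents leave open.

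At the low use that discouragement should produce, the cost beyond lost sample is modest: roughly 2 to 5 power points. At higher pain-driven use it is roughly 4 to 15 points. Inflated false positives need use that both follows pain and differs by arm. All of this assumes 1:1 allocation, a normal score, a 0.74 SD effect and the usage rates shown, none of which the plan supplies. Confidence is medium. The change should be made because it is cheap and because evening PPPM data not collected cannot be recovered.

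**What to change.** Replace the withdrawal sentence in Study Population, item 5, and in Risks, item 5, with wording such as:

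> Children given post-operative Precedex or Ketorolac remain in follow-up (post-operative FLACC, PACU time, evening PPPM) and are analysed in the arm to which they were randomised. The drug and its time relative to the FLACC are recorded and reported by arm. The primary analysis estimates the effect of assignment to LA regardless of these drugs. An analysis excluding recipients is a sensitivity analysis.

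State this openly as a choice of question: excluding recipients asks about LA in the absence of these drugs. In Risks, item 5, the sentence that limits withdrawal to children needing extraction must also be reconciled with whatever grounds remain. Clinicians' decisions about the drugs are unaffected.

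The cost is protocol wording, with no extra children or visits. FLACC is routine and copied from the chart (Study Procedures, item 7; Secondary Data/Specimen Details, item 1), and the evening call is already planned. Its PPPM questions are asked only for research, so that score is lost if the parent is not asked. The anesthesia record is already reviewed (HIPAA Privacy Board Requirements, item 2), and the listed anesthesia data form, which is not visible here, may already capture drug and time; if not, one field is added. The drawback is that scores taken after the drug reflect LA plus the drug.
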